2 STUDY DESCRIPTION

2.1 Study Design

This is an open-label, multicenter phase I/II study of nivolumab in combination with brentuximab vedotin designed to evaluate the safety and efficacy in subjects with NHL subtype of DLBCL, PTCL (excluding ALCL), PMBL, MGZL and CTCL(MF/SS).

The study will consist of three phases: Screening, Treatment and Follow-up. The treatment phase is divided in two parts: Cohort A consists of the Dose Evaluation Phase and Cohort B is the Expansion Phase.

It is anticipated that 170 subjects will be enrolled in the United States, Canada and Europe for the entire study (Cohort A and Cohort B combined). All subjects will undergo a screening period to determine eligibility within 28 days prior to initial dosing.

Dose Evaluation Phase (Cohort A)

The Dose Evaluation Phase (Cohort A) will include a dose limiting toxicity (DLT) evaluation for the dose level of brentuximab vedotin 1.8mg/kg intravenously in combination with nivolumab 240mg flat dose intravenously in a q 3 week cycle.

In cycle 1, brentuximab vedotin 1.8mg/kg will be administered on day 1 where as nivolumab 240mg flat dose will be administered on day 8. Subsequent to cycle 1, both drugs will be administered on the first day of the new cycle. Brentuximab vedotin will be administered first as a 30-minute infusion followed by a minimum 30-minute rest. Nivolumab will then be administered also as a 30-minute infusion.

The DLT evaluation period, which consists of the first dose of study drug through the first 6 weeks of treatment, will be conducted in the first 6 treated subjects (all comers). Decisions to enroll up to 6 additional subjects onto the same dose of brentuximab vedotin 1.8mg/kg in combination with nivolumab 240mg flat dose intravenously every 3 weeks or at a reduced dose of brentuximab vedotin at 1.2mg/kg will be based on the safety data reviewed throughout the DLT evaluation period. After 6 DLT-evaluable subjects have been followed through the first 6 weeks of treatment, or at the point that 2 or more subjects experience a DLT, whichever comes first, the study team will review the available data and provide recommendations.

Expansion Phase (Cohort B)

The Expansion Phase will assess the combination of nivolumab and brentuximab vedotin and will consist of a single-arm phase II study which will expand enrollment at the recommended dose level and treatment schedule as deemed safe by the study team in Cohort A. An additional 40 subjects in DLBCL (cohort B1), 30 subjects in PTCL (cohort B2), 20 subjects in CTCL (cohort B3) 30 subjects in PMBL (cohort B4) and 10 subjects in MGZL (cohort B5) will be enrolled to complete this evaluation.

All subjects in Cohort A and Cohort B will be allowed to be treated until disease progression or unacceptable toxicity as described in Protocol Section 4.5.3 and Section 4.5.5. If during therapy it

appears that a subject is benefiting from the combination but experiencing toxicities related to one agent that would require permanent treatment discontinuation, then they have the option to continue therapy with the single agent not attributing to toxicities.

Subjects that present progressive disease during treatment may be allowed to be treated beyond progression until further progression is observed.

Once subjects discontinue from study treatment for any reason, subjects will enter the follow-up phase of the study.

The study design schematic is presented in Figure 2.1-1

Figure 2.1-1:Study Design Schematic

2.2 Treatment Assignment

After the subject's initial eligibility is established and informed consent has been obtained, the subject must be enrolled into the study by calling an IVRS to obtain the subject number. Every

subject that signs the informed consent form must be assigned a subject number in IVRS. Specific instructions for using IVRS will be provided to the investigational site in a separate document.

2.3 Blinding and Unblinding

Not applicable. This is an open-label study.

2.4 **Protocol Amendments**

Amendments 01, 02 and 03 are site specific.

This SAP is based on the Revised Protocol 01 dated 14-Sep-2016. It incorporates Amendment 04. This amendment allowed additional cohorts of subjects with relapsed PMBL & MGZL to participate in the expansion cohort. Additionally, the amendment also defined Indeterminate response (IR) criteria and described changes in the biomarker section. Minor clarification in the inclusion, exclusion criteria and clarification of dose adjustment for brentuximab vedotin for grade 3 neurological toxicity have also been made.

The SAP will be updated in the future if any amendment to the protocol is made that has impact on the analyses.

2.5 Data Monitoring Committee

Not applicable.

3 OBJECTIVES

3.1 Primary

To evaluate the safety and tolerability of the combination of nivolumab and brentuximab in subjects with the diagnosis of relapsed, refractory DLBCL, PTCL (all subtypes excluding ALCL) and PMBL, MGZL and CTCL(MF/SS)

To assess the clinical benefit of nivolumab and brentuximab vedotin combination regimen in subjects with the diagnosis of relapsed/refractory DLBCL, relapsed/refractory PTCL (excluding ALCL), relapsed/refractory PMBL, relapsed/refractory MGZL and relapsed/refractory CTCL (MF/SS) (CD30 expression $\geq 1\%$ by IHC is a prerequisite for all subjects participating in this study), as measured by ORR, defined as the proportion of subjects achieving either a PR or CR.

3.2 Secondary

- To assess overall duration of response (DOR) of the brentuximab vedotin and nivolumab combination regimen based on investigators assessments
- To assess the complete response rate (CRR) with the combination regimen and the duration of CR based on investigators assessments.
- To assess PFS based on investigator assessment and OS of the brentuximab vedotin and nivolumab combination regimen.

4 ENDPOINTS

4.1 **Primary Endpoints**

The primary safety endpoints include DLT, incidence of deaths, adverse events, serious adverse events, adverse events leading to discontinuation, adverse events leading to dose delay, drug-related adverse events and specific laboratory abnormalities (worst grade). Toxicities will be graded using the National Cancer Institute (NCI) Common Terminology Criteria for Adverse Events (CTCAE) version 4.03.

The primary efficacy endpoint is ORR. It is defined as the number of subjects with a best overall response (BOR) of CR or PR divided by the number of treated subjects. The BOR is defined as the best response designation recorded between the date of first dose and the date of initial objectively documented progression or the date of subsequent therapy, whichever occurs first. Allogeneic SCT and ASCT will be considered as subsequent therapy. In subjects with relapsed refractory DLBCL, relapsed refractory PMBL, relapsed refractory MGZL and relapsed refractory PTCL the response (CR, PR, SD and progression) will be assessed according to Lugano Classification 2014. A CR must have been confirmed by scans, including a negative Positron Emission Tomography (PET) to be considered for CR in subjects with PTCL, PMBL, MGZL and DLBCL. For subjects with relapsed refractory CTCL, response will be assessed according to consensus Global Response Score as per the consensus statement of the International Society for Cutaneous Lymphoma.

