Laboratory Tests	X		Required for X01: CBC with differential, uric acid, serum urea level, serum creatinine, sodium, potassium, calcium, magnesium, chloride, glucose, AST, ALT, total bilirubin, alkaline phosphatase, LDH, TSH (reflex to free T3, free T4 for abnormal TSH result). Panel should also be performed at X02 if X01 results were abnormal.
Pregnancy Test (WOCBP only)	X		Serum or urine

Table 5.1-3: Follow-up Assessments (CA209436)			
Follow-up Assessments (CA209436)			
Procedure	Follow Up, Visits 1 and 2^a (X01 & X02)	Survival Follow-Up Visits^b	Notes
Efficacy Assessments			
Radiographic Tumor Assessment CT chest, CT/MRI abdomen, pelvis, and any other known sites of disease FDG PET-CT (DLBCL, CTCL, PMBL & MGZL only)	X	X	Only for subjects without documented progression since first dose of study therapy Tumor assessments will occur at Week 6 and Week 12 continuing every 9 weeks (+/- 1 week) for the subsequent 4 tumor assessment timepoints, regardless of dosing schedule. After the first year, tumor assessments are to occur every 12 weeks (+/- 2 weeks) until disease progression is documented. FDG PET-CT is required for assessment of DLBCL/PTCL/PMBL/MGZL subjects NOTE: Subjects proceeding to allogeneic SCT or ASCT will be assessed on Day 100, at 6 months, 1 year and every year thereafter from the date of stem cell infusion until the first non-CR after SCT is documented. Refer to section 5.4 for further details.
Blood tumor burden assessment (SS-CTCL only)	See note	See note	Only required to confirm CR in CTCL SS subjects in case blood was positive for tumor cells at screening. Refer to section 5.4.3.6 for details.
Modified Severy Weighted Assessment Tool for subjects with Cutaneous T Cell Lymphoma	See note	See note	Required for subjects with Cutaneous T Cell Lymphoma as part of disease assessment. Refer to Appendix 4 for details.
Medical Photography	See note	See note	Suggested for subjects with Cutaneous T Cell Lymphomas as part of disease assessment. To be done along with the radiographic assessment for all of those respective timepoints. Refer to section 5.4.3.5 for details.

Table 5.1-3: Follow-up Assessments (CA209436)			
Follow-up Assessments (CA209436)			
Procedure	Follow Up, Visits 1 and 2^a (X01 & X02)	Survival Follow-Up Visits^b	Notes

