5.4 Efficacy Assessments

DLBCL, PTCL, PMBL and MGZL Efficacy Assessment:

The primary efficacy assessment is Objective Response (OR). Objective Response is defined as a subject achieving either a PR or CR according to the Lugano Classification 2014 and Lymphoma Response to Immunomodulatory therapy Criteria (LYRIC) ([Appendix 2](#)) and will be based on investigator assessed response. Efficacy assessment for DLBCL, PTCL, PMBL and MGZL will be primarily derived from the FDG PET-CT performed according to the timepoints described in [Table 5.1-1](#) [Table 5.1-2](#) and [Table 5.1-3](#). Subjects with PET-Avid lesions at baseline should be followed with PET, subjects with non-Pet avid lesions and lesions on CT scans at baseline should be followed with CT Scans. Tumor assessment (CR or non-CR) will be assessed by the investigator according to the Lugano Classification 2014.

CTCL Efficacy Assessment:

Efficacy assessment for Cutaneous T Cell lymphomas will include CT/MRI for visceral disease assessment and peripheral lymph nodes at the pre-determined timepoints described in [Table 5.1-1](#) [Table 5.1-2](#) and [Table 5.1-3](#). The consensus Global Response Score assessment to evaluate disease activity will also be completed at every tumor assessment time point to assess extent of disease. Medical photographs are recommended to document the appearance of skin lesions throughout the study. The mSWAT will be used to assess skin involvement, it is preferable that the mSWAT assessments should be performed by the same investigator at all time points to eliminate inter-

observer variability for a given patient. Lymphoma Response to Immunomodulatory therapy Criteria (LYRIC) will be used where clinically indicated ([Appendix 2](#)).

Whole blood must be included for assessment of SS-CTCL at baseline to evaluate blood tumor burden. In the case the blood is confirmed to be positive for tumor cells, it must be reassessed at the time of response documentation, prior to its confirmation.

All subjects treated are expected to be followed for disease progression. Subjects that discontinue treatment for other reasons different from disease progression must continue to perform tumor assessments as described in [Table 5.1-3](#) until disease progression is documented.

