5.4.1 Radiographic Assessments

Baseline assessments should be performed within 28 days prior to the first dose, utilizing FDG PET-CT, CT or MRI. CT scans are preferred for CTCL. In addition to chest, abdomen, pelvis, all known sites of disease should be assessed at baseline. FDG PET-CT will be performed for assessment throughout the study for subjects with DLBCL, PTCL, PMBL and MGZL. Low dose or attenuation correction CT portions of a combined FDG PET-CT are of limited use in anatomically based efficacy assessments and it is therefore suggested that they should not be substituted for dedicated diagnostic contrast enhanced CT scans for anatomically based measurements. However, if a site can document that the CT performed as part of a FDG PET-CT is of identical diagnostic quality to a diagnostic CT with oral contrast, (+/- IV contrast) then the adequate dose CT of the FDG PET-CT can be used for tumor measurements. Subjects with CTCL are to perform the CT scans described above in addition to medical photographs if appropriate for disease assessment.

Subjects will be evaluated for tumor response by FDG PET-CT, or CT/MRI at week 6 and week 12 continuing every 9 weeks (+/- 1 week) for the subsequent 4 tumor assessment timepoints, regardless of dosing schedule. After the first year, tumor assessments are to occur every 12 weeks (+/- 2 weeks) until disease progression is documented.

Tumor assessments for ongoing study treatment decisions will be completed by the investigator using the Lugano Classification 2014 for Diffuse Large B Cell Lymphomas and Peripheral T Cell Lymphomas. Refer to [Appendix 2](#) for further details. For Cutaneous T Cell Lymphomas, response

should be assessed by the consensus Global Response Score. Refer to [Appendix 4](#) for further details.

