5.4.3.3 FDG PET-CT, CT Scan and MRI

Contrast-enhanced Computed Tomography (CT) scans acquired on dedicated CT equipment are preferred for response assessment of subjects with CTCL or DLBCL/PTCL/PMBL/MGZL subjects without FDG avid tumors in this study. CT with contrast of the chest, abdomen and pelvis (as clinically indicated) are to be performed for tumor assessments at week 6 and week 12 continuing every 9 weeks (+/- 1 week) for the subsequent 4 tumor assessment timepoints, regardless of dosing schedule. After the first year, tumor assessments are to occur every 12 weeks (+/- 2 weeks) until disease progression is documented. CT scans should be acquired with 5mm slices with no intervening gap (contiguous). When CT scans have slice thickness greater than 5 mm, the minimum size for a measurable lesion should be twice the slice thickness.

Should a subject have a contraindication for CT IV contrast, a non-contrast CT of the chest and a contrast enhanced MRI of the abdomen and pelvis may be obtained. MRIs should be acquired with slice thickness of 5 mm with no gap (contiguous).

Every attempt should be made to image each subject using an identical acquisition protocol on the same scanner for all imaging time points.

FDG PET-CT with oral contrast and intravenous contrast will be performed for assessment throughout the study for patients with DLBCL, PTCL, PMBL and MGZL. If however CT is low dose and intravenous contrast is not available, then sites may obtain additional CT with oral and intravenous contrast.

Note on CT component of a PET-CT scanner: Combined modality scanning such as with PET-CT is increasingly used in clinical care. Low dose or attenuation correction CT portions of a combined PET-CT are of limited use in anatomically based efficacy assessments and it is therefore suggested that they should not be used. Site should document that the CT performed as part of a PET-CT is of identical diagnostic quality to a diagnostic CT (with IV and oral contrast). In certain cases where the CT portion of the PET-CT scan is low dose, then a diagnostic CT scan with oral and intravenous contrast should be performed.

MRI of the brain should be done at baseline if CNS involvement is suspected to rule out active disease. Scans during on-study treatment and follow up periods are required only as clinically indicated for new signs and symptoms that suggest central nervous system (CNS) involvement.

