8.3 Endpoints

8.3.1 Primary Endpoint(s)

The primary safety endpoints include incidence of deaths, adverse events, serious adverse events, adverse events leading to discontinuation, adverse events leading to dose delay, drug-related adverse events and specific laboratory abnormalities (worst grade). Toxicities will be graded using the National Cancer Institute (NCI) Common Terminology Criteria for Adverse Events (CTCAE) version 4.03.

The primary efficacy endpoint is ORR. It is defined as the number of subjects with a best overall response (BOR) of confirmed CR or PR divided by the number of treated subjects. The BOR is defined as the best response designation recorded between the date of first dose and the date of initial objectively documented progression or the date of subsequent therapy, whichever occurs first. Allogeneic SCT and ASCT will be considered as subsequent therapy. In subjects with relapsed refractory DLBCL, relapsed refractory PTCL, relapsed refractory PMBL and relapsed refractory MGZL the response (CR, PR, PD, and progression) will be assessed according to Lugano Classification 2014. For subjects with relapsed refractory CTCL, response will be assessed according to consensus Global Response Score as per the consensus statement of the International Society for Cutaneous Lymphoma. A CR must have been confirmed by scans, including a negative Positron Emission Tomography (PET) to be considered for CR in subjects with PTCL, DLBCL, PMBL and MZGL. In subjects with PTCL, if the bone marrow was compromised at baseline, a bone marrow must also be negative at the time of CR. In CTCL CT scans (chest, neck, abdomen and pelvis), blood flow for SS cells and m SWAT skin scoring along with medical photography will be performed at baseline and at the end of the treatment for response evaluation. The investigator will perform tests that will allow evaluation of response to therapy according to corresponding disease criteria in [Appendix 2](#) and [Appendix 4](#). The analysis of the primary endpoint will occur approximately 8 months after the last enrolled subject's first dose of study therapy. Depending on the enrollment for each disease cohort, the analysis may be done at different times for each cohort, or at the same time for the three cohorts.

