*A score of 3 in many patients indicates a good prognosis with standard treatment, especially if at the time of an interim scan. However, in trials involving PET where de-escalation is investigated, it may be preferable to consider a score of 3 as inadequate response (to avoid undertreatment). Measured dominant lesions: Up to six of the largest dominant nodes, nodal masses, and extranodal lesions selected to be clearly measurable in two diameters. Nodes should preferably be from disparate regions of the body and should include, where applicable, mediastinal and retroperitoneal areas. Non-nodal lesions include those in solid organs (eg, liver, spleen, kidneys, lungs), GI involvement, cutaneous lesions, or those noted on palpation. Nonmeasured lesions: Any disease not selected as measured, dominant disease and truly assessable disease should be considered not measured. These sites include any nodes, nodal masses, and extranodal sites not selected as dominant or measurable or that do not meet the requirements for measurability but are still considered abnormal, as well as truly assessable disease, which is any site of suspected disease that would be difficult to follow quantitatively with measurement, including pleural effusions, ascites, bone lesions, leptomeningeal disease, abdominal masses, and other lesions that cannot be confirmed and followed by imaging. In Waldeyer's ring or in extranodal sites (eg, GI tract, liver, bone marrow), FDG uptake may be greater than in the mediastinum with complete metabolic response, but should be no higher than surrounding normal physiologic uptake (eg, with marrow activation as a result of chemotherapy or myeloid growth factors).

†PET 5PS: 1, no uptake above background; 2, uptake ≤ mediastinum; 3, uptake > mediastinum but ≤ liver; 4, uptake moderately > liver; 5, uptake markedly higher than liver and/or new lesions; X, new areas of uptake unlikely to be related to lymphoma.

*The recommendations from Lugano Classification is to use a 5 point scale to assess the metabolic response in PET-CT based response.

Response Evaluation in DLBCL, PTCL, PMBL & MGZL:

CR (Complete Remission)

The designation of CR requires all of the following be met:

- 1) Complete disappearance of all detectable clinical evidence of disease.
 - a) PET-CT-based response: A score of ≤ 3 is considered to represent complete metabolic response.

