 - b) CT based response: Target node/nodal masses must regress to ≤ 1.5 cm in LDi, with no extralymphatic sites of disease.

Organ involvement: Absence of organomegaly (Table 3).

- 2) Bone marrow: No evidence of FDG-avid disease in marrow. If there was evidence of involvement of bone marrow with lymphoma at screening/baseline and a biopsy was performed (PTCL), a bone marrow biopsy will be required to confirm CR.
- 3) The presence of residual symptoms in the absence of detectable disease by imaging does not preclude the designation of CR.

PR (Partial Remission)

The designation of PR requires all of the following:

- 1) PET-CT based response: Score of 4 or 5, provided reduced uptake compared with base line and absence of structural progression development on CT Scan.

- 2) CT based response: $\geq 50\%$ regression in SPD of upto 6 measurable nodal and extranodal lesions (Table 3) .
- 3) Splenic and hepatic nodules must regress by $\geq 50\%$ in length beyond normal.

Bone marrow : reduced uptake compared with baseline. If there is evidence of nodal response but persistent focal changes in the marrow consider further evaluation (Table 3).

SD (Stable Disease)

SD is defined as the following:

- 1) PET-CT based response: no metabolic response, score of 4 or 5 with no significant changes from baseline.
- 2) CT based response: $< 50\%$ decrease from baseline, absence of new lesions (Table 3).
- 3) Bone marrow: no change from baseline.

PD: Relapsed Disease (after CR)/Progressive Disease (after PR, SD)

- 1) PET-CT based response: Score of 4 or 5 with increase in intensity from baseline or interim scan/ or any new FDG avid focus consistent with malignant lymphoma (Table 3).
- 2) CT based response: New node, new or recurrent splenomegaly, progression of existing lesions (Table 3).

IR (INDETERMINATE RESPONSE)

A patient will be considered to have Indeterminate Response (IR) in one or more of the 3 following circumstances

- 1) Increase in overall tumor burden (as assessed by SPD) of $\geq 50\%$ of up to 6 measurable lesions in the first 12 weeks of therapy, without clinical deterioration (IR(1))
- 2) Appearance of new lesions; or growth of one or more existing lesion(s) of $\geq 50\%$ at any time point during treatment occurring in the context of lack of overall progression ($<50\%$ increase) of overall tumor burden, as measured by SPD of up to 6 lesions at any time during the treatment (IR(2))

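### The negative-PET condition for CR is not reconciled with CT follow-up of subjects whose disease is not PET-avid

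*SAP*

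**What the plan says.** SAP 4.1 sets the condition for a complete response in the four lymphoma types assessed by Lugano 2014 (DLBCL, PTCL, PMBL, MGZL): "A CR must have been confirmed by scans, including a negative Positron Emission Tomography (PET) to be considered for CR". Protocol 8.3.1 has the same sentence. CTCL is assessed by the Global Response Score and is not covered by it.

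Protocol 5.4 and Table 5.1-2 assign the imaging method by baseline avidity. Subjects with avid lesions are followed with PET, while "subjects with non-Pet avid lesions and lesions on CT scans at baseline should be followed with CT Scans". Protocol 5.4.3.3 adds that contrast CT scans "are preferred for response assessment of subjects with CTCL or DLBCL/PTCL/PMBL/MGZL subjects without FDG avid tumors in this study".

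Appendix 2 describes CR by both methods. For PET-CT: "A score of ≤ 3 is considered to represent complete metabolic response". For CT: "CT based response: Target node/nodal masses must regress to ≤ 1.5 cm in LDi, with no extralymphatic sites of disease".

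SAP 4.2 defines the CR rate as subjects with a best overall response (BOR) of CR over all treated subjects, and evaluates duration of CR only in subjects with a BOR of CR. SAP 7.5.2 analyses the CR rate in the same way as ORR, with a two-sided 80% Clopper-Pearson interval.

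**The concern.** The protocol foresees subjects without avid disease, sends them to CT and supplies CT criteria for a complete response. The endpoint definition then makes CR depend on a scan that this follow-up rule does not assign to them. No section says how to score a subject who meets the CT criteria and has no PET at response.

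At stake are two secondary endpoints, CR rate and duration of CR, and the split between CR and PR in the BOR table. A subject denied CR leaves the CR numerator and also the set in which duration of CR is estimated. Sites and programmers could settle the matter differently, so the same CT finding might be counted in two ways within one cohort.

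**Working it through.** **No stated figure to reproduce.** The plan gives no target, null or power for the CR rate, and no share of non-avid subjects. The interval method that CR shares with ORR can be checked. Two-sided 80% Clopper-Pearson gives 48.6-70.6% for 24/40, 46.7-72.3% for 18/30, 37.0-63.0% for 15/30 and 11.6-55.2% for 3/10, all matching SAP Table 5.1-1.

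**Inputs for a sensitivity range**
- p, the true CR rate. Low anchor 17%, the CR rate quoted in protocol 1.1.1 for single-agent brentuximab vedotin in DLBCL. High value 40%, an assumption.
- f, the share of subjects with non-avid disease. Not in the documents; assumed 2.5-20%, with 5-10% as the working range. CR is taken as equally likely in avid and non-avid subjects, so f is also their share among complete responders.
- u, the share of non-avid complete responders with no PET at response. u = 1 is the literal worst case. Any PET that is done is taken to read negative.

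**Formula.** Reported CR rate = p × (1 − f × u), so shortfall = p × f × u.

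With u = 1, in percentage points:

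| f | p = 17% | p = 40% |
|---|---|---|
| 2.5% | 0.17 × 0.025 = 0.4 | 0.40 × 0.025 = 1.0 |
| 5% | 0.17 × 0.05 = 0.85, about 0.9 | 0.40 × 0.05 = 2.0 |
| 10% | 0.17 × 0.10 = 1.7 | 0.40 × 0.10 = 4.0 |
| 20% | 0.17 × 0.20 = 3.4 | 0.40 × 0.20 = 8.0 |

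With u = 0.5 every entry halves. With u = 0 or f = 0 the shortfall is zero.

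**In subjects.** Only non-avid subjects who reach a complete response can be misclassified. In a cohort of 30 with u = 1, the expected number is 30 × 0.05 × 0.17 = 0.26 to 30 × 0.10 × 0.17 = 0.51 at a 17% CR rate, and 30 × 0.05 × 0.40 = 0.6 to 30 × 0.10 × 0.40 = 1.2 at 40%.

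**One subject reclassified.** The CR rate moves by 1/40 = 2.5 points, 1/30 = 3.3 points or 1/10 = 10 points at the planned Cohort B sizes. SAP 7.1 pools Cohort A subjects by subtype, so actual denominators may be slightly larger. In the interval, going from 12/30 to 11/30 changes 27.7-53.3% to 24.8-50.0%, and going from 4/10 to 3/10 changes 18.8-64.6% to 11.6-55.2%.

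**ORR.** CR and PR both count as response, so moving a subject from CR to PR leaves the ORR numerator unchanged.

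**The case against.** The strongest reply is that PET is called for in everyone with these four types. Protocol 5.4.1 says "FDG PET-CT will be performed for assessment throughout the study for subjects with DLBCL, PTCL, PMBL and MGZL", 5.4.3.3 repeats it, and the follow-up schedule in Table 5.1-3 says "FDG PET-CT is required for assessment of DLBCL/PTCL/PMBL/MGZL subjects". For non-avid tumours CT is only preferred, or what should be used; nothing says PET is omitted. A non-avid subject who does have a PET could score 3 or less and so satisfy the condition. Moreover, SAP 4.1 and 4.2 rest response and CR rate on Lugano 2014, and the Appendix 2 table has a CT column for complete response. The endpoints concerned are secondary and descriptive.

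Much of this stands. A reader might infer that non-avid subjects can never be scored CR, or that the CR rate is biased down as a matter of course. The documents support neither. The loss needs a non-avid subject, a complete response on CT, no PET at that time, and the PET sentence applied over the CT criteria. If any one of these is absent, nothing is lost. A reader might also infer that such a subject is recorded as PR; that is plausible, but no section says it. Nor should all non-avid subjects be counted as affected, since most may not reach a complete response.

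The reply does not remove the conflict. The general PET sentences contradict the specific instruction to follow non-avid disease with CT, and protocol 5.4.1 itself also allows evaluation by CT or MRI. A negative PET in disease that was never avid meets the condition without measuring response. The Lugano route does not settle it either. In SAP 4.1 the PET sentence follows the Lugano sentence as a further condition, and the CR text in Appendix 2 places the PET and CT criteria together under a requirement that every item be met.

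**Conclusion.** The inconsistency is real and minor. Read literally, protocol 8.3.1 and SAP 4.1 withhold CR from a non-avid subject with a complete radiologic response on CT and no PET at response, so any resulting error in the CR rate can only be downward. Duration of CR and the BOR table are affected with it. The primary ORR is unaffected provided the subject is counted as PR, and CTCL is outside the rule.

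The size cannot be established from the documents. On an assumed non-avid share of 5-10%, equal CR rates and no PET at response, it is about 0.9-1.7 points at a 17% CR rate and 2-4 points at an assumed 40%. It is zero where a PET is done and reads negative. In one small cohort the effect would appear as a single subject, most visibly in MGZL, where one subject is 10 points.

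**What to change.** Amend the CR condition in both protocol 8.3.1 and SAP 4.1; changing only one would leave the conflict in place. Require a negative PET for CR in subjects with FDG-avid disease at baseline. For subjects followed by CT because their disease was non-avid at baseline, apply the Appendix 2 CT-based CR criteria, and say that these apply on their own. Report the number of such subjects in each cohort.

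The cost is one clause in each document and one row in a table. SAP 7.3.2 already plans to tabulate baseline PET status and the 5-point score, so the count should need little or no new data. The clause should be settled before CR is derived.
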